2. On the day of the run, remove the 6 vials for the appropriate run. Immediately place the box with the unused vials back in the freezer. Allow the vials to thaw at room temperature or in a 25°C water bath for 30 minutes. Mix the serum by gentle inversion 2-3 times during this period. Just before pipetting, mix the sample again by gentle and thorough swirling or on a blood mixing wheel or a similar device for five minutes. Do not vortex or shake the serum vigorously. Be certain that the serum appears homogeneous before sampling.
3. Take two aliquots from each vial and analyze for HDL-cholesterol. The aliquots should be treated the same as independent patient specimens and should be randomly distributed throughout the other patient specimens in the run.
4. Record the results on the forms provided. Be certain to correctly transcribe the 6 digit code from each CDC vial to the data form under "HDL Vial #".

Delta Project
Laboratory Precision Evaluation

Total Cholesterol

Laboratory Name: _____

Run 1		Date: _____		
TC Vial #	Results			

Run 2		Date: _____		
TC Vial #	Results			

Run 3		Date: _____		
TC Vial #	Results			

Return this form to: [name] [contact]
Copy to: [name] [contact]

Delta Project
Laboratory Precision Evaluation

HDL - Cholesterol

Laboratory Name: _____

Run 1	Date: _____	
HDL Vial #	Results	

Run 2	Date: _____	
HDL Vial #	Results	

Run 3	Date: _____	
HDL Vial #	Results	

Return this form to: [name] [contact]
Copy to: [name] [contact]

DELTA PROJECT - TOTAL CHOLESTEROL PRECISION

within laboratory

lab	pool 66 mean	CV	pool 67 mean	CV	pool 71 mean	CV
colu	183	0.7	220	0.9	274	0.6
loui	178	0.9	216	1.0	263	0.7
mibh	182	1.3	219	1.2	274	1.2
minn	175	1.9	210	1.6	257	1.6
stan	184	0.4	220	0.6	272	0.5
	180.4	1.1	217.0	1.1	268.0	0.9
CDC Mean	183		220		273	

DELTA PROJECT - HDL PRECISION

within laboratory

lab	pool 36 mean	CV	pool 81 mean	CV	pool 88 mean	CV
colu	60	0.9	40	1.3	27	1.9
loui	56	1.9	38	1.4	27	2.1
mibh	60	2.0	40	2.0	28	2.2
minn	53	1.5	36	1.3	25	1.3
stan	60	1.1	41	0.8	29	0.9
	57.8	1.5	39.0	1.4	27.2	1.7
CDC mean	59.0		39.6		27.2	

DELTA PROJECT - TOTAL CHOLESTEROL PRECISION

	POOL 66 VARIANCE	CV	% TOTAL	POOL 67 VARIANCE	CV	% TOTAL	POOL 71 VARIANCE	CV	% TOTAL	MEAN CV	MEAN % TOTAL
TOTAL	17.1	2.3	100	22.2	2.2	100	63.3	3.0	100	2.5	100
LAB	12.1	1.9	71	15.3	1.8	69	55.3	2.8	87	2.2	75.7
RUN	2.4	0.9	14	4.5	1.0	20	3.1	0.7	5	0.8	13.0
REPS.	2.6	0.9	15	2.5	0.7	11	4.9	0.8	8	0.8	11.3
MEAN	180.26			217.1			268.4				

DELTA PROJECT - HDL PRECISION

	POOL 36 VARIANCE	CV	% TOTAL	POOL 81 VARIANCE	CV	% TOTAL	POOL 88 VARIANCE	CV	% TOTAL	MEAN CV	MEAN % TOTAL
TOTAL	1.4	5.9	100	4.1	5.2	100	3.0	6.3	100	5.8	100
LAB	.6	5.6	93	3.8	5.0	92	2.7	6.1	92	5.6	92.3
RUN	.2	0.7	1	0.1	0.7	2	0.0	0.6	1	0.7	1.3
REPS.	0.7	1.4	6	0.2	1.3	6	0.2	1.7	7	1.5	6.3
MEAN	57.7			38.7			27.2				

Variance components shown above are total, among labs, among runs-within labs, and among replicates.

Analysis of precision data for delta project:

An analysis of variance of the reported concentrations from laboratories was done to study the source of variability. For TC, 75% of total variation was due to among-lab differences, and this was 92% for HDL. The within-lab CV averages about 1% for TC and 1.5% for HDL for these laboratories.

For TC, the Minn lab had the highest CV for TC (~1.7%), while the Mibh lab had the highest CV for HDL (~2.1%). The Stan lab had the best precision for both TC and HDL.

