2.4 Edits

Each data field that you enter has an associated status byte vector which gives additional information about the field, for example, whether the field is empty, is missing, or contains an out of range value. The Problem selection on the Add and Browse menus gives you a way to provide this additional information.

As you enter data values into the form they are edited. If you do not have modify privileges, you will be alerted:

```
YOU ARE NOT AUTHORIZED TO MODIFY RECORDS
-----
Press any key to continue....
```

The old value will be replaced.

If a value fails an edit, for example if it is out of range or inconsistent with other values, an error window alerts you and gives the valid range:

```
INVALID: Valid values are: YN.
-----
Press any key to continue....
```

Press any key to clear the error and return to the field. If you made a keying mistake, retype the value. However, if the value is correct you must confirm it. Use the Problem menu to do this:

Confirm value	CTRL+F
Questionable log	CTRL+Q
Note log	CTRL+N
Unresolvable field	CTRL+U
Reset field to blank	CTRL+T
Print form	CTRL+I

Choose **Confirm** to confirm that an out of range value is accurate by setting the first status byte to 'C'.

Use **Unresolvable** when a value cannot be collected or when the value you did collect is suspicious and should not be used in analysis. **Unresolvable** sets the first status byte to 'U' and, if the field is blank, fills the field with equal signs (==). Note that you can set a field to Unresolvable by keying the equal signs into the field rather than using the Problem menu.

Reset removes the value in the field and sets the first status byte back to 'E' (empty).

Questionable and **Note** allow you to comment on a field to explain a response or to enter a response that will not fit into the field. Choosing either option opens a window in which you can type comments.

Save Cancel Delete

==== Questionable Log for field: LIPAI =====

If a note or questionable log has already been entered for the field, it is shown in the window. You can add to the end of the existing text. The window is empty if no log exists for the field.

There are four options on the menu bar. Choose **Delete** to delete the log displayed. To leave the log window without saving changes, select **Cancel**. Choose **Save** to save changes and return to the form. To print the log, choose **Print**.

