Estradiol will be measured by an RIA method using ¹²⁵I tracer (Coat-a-Count from Diagnostic Products Corporation, Los Angeles, CA). This method is a solid phase

assay with virtually no cross reactivity with other steroid hormones. The assay uses 100 ul of serum or plasma and the analyte is stable for six months at -80°C.

Reference ranges

Early follicular	30-100 pg/ml
Late follicular	100-400 pg/ml
Luteal	50-150 pg/ml

c. Luetinizing Hormone (LH)

LH will be measured by an RI method using ¹²⁵I tracer (Coat-a-Count from Diagnostic Products Corporation, Los Angeles, CA). This method is a solid phase assay with virtually no cross reactivity with other steroid hormones. The assay uses 100 ul of serum or plasma and the analyte is stable for six months at -70°C. LH maintains a low and constant level in the blood during the follicular phase, rise rapidly at ovulation and fall to a constant level during the luteal phase. The rise of LH at ovulation is of about a three-day duration.

Reference ranges

Follicular	0-14 mIU/mL
Midcycle peak	20-70 mIU/mL
Luteal	0-16 mIU/mL

VII. QUALITY CONTROL PROCEDURES

A. Overview

To assure validity of the results in this study requires rigid adherence to collection, labeling, and shipping protocols. To ensure that these are well understood, a training session will be held to provide training and experience before the beginning of the project. Adherence to these protocols, including periodic reviews and retraining, are the responsibility of each field center.

In addition, other quality control measures will be taken to assess the integrity of the stored samples once they are removed from storage for analysis (sections VI.B and C.) in addition to individual laboratory quality control programs that are in place for each analyte (section VI.D.).

B. Sample Integrity

Aliquots of samples will be frozen upright at -80°C before being placed in boxes for long-term storage and shipping. Upon removal from freezers for shipping or analysis, the sample should be inspected to for evidence of thawing and leaking. If the liquid is no longer frozen (with top of frozen layer being horizontal in the vial) in the bottom of the vial or if there is evidence that the sample has leaked, based on less than the original volume remaining in the vial, the sample will be discarded and replaced by another sample that is acceptable.

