Upon receipt at local or central laboratories, samples will be inspected upon unpacking to assure that they remained frozen in transit. Any sample showing evidence of being thawed will be noted. If transportation to the local laboratory occurs immediately upon removal from the -80°C freezer (within three hours) the sample needs to be kept frozen. Any sample that showed evidence of thawing but remained cold during transport may be analyzed for lipids and lipoproteins, but not for coagulation factors. Analysis should occur within three days of receipt of these samples. Any sample that leaked during transport will not be analyzed.

Any sample that has been identified as thawed will not be included in the data analysis if the analytical results are greater than 3SD (biologic plus analytical) from the average of the other three in that set of four.

Expected biologic plus analytical SD for triplicate analysis (Clin. Chem. 36,209, 1990)

1 SD

Cholesterol	5%
Triglyceride	13%
HDL-chol	7%
Apo A-1	10%
Apo B-100	11%

Sample identity will also be verified based on packing lists and FAXed inventory lists. Any shipment that shows a discrepancy between the packing list and the actual contents may be sent back to the originating center to correct if the discrepancy cannot be resolved by a phone call.

C. Analytical Integrity

Samples will be coded such that all samples from a single subject can be identified and grouped into three sets, from each of the three diet phases. These will be analyzed for each analyte on a single run for the analyte. If any sample of a set from the end of a single diet trial is more than 3SD (biologic plus analytical) from the average of the others, it will be reanalyzed promptly to confirm the value. It is the responsibility of the laboratory performing each test to review results on a run to run basis to identify such outliers and schedule a repeat analysis.

D. Analytical Quality Control Procedures

All analytical runs will include appropriate quality control samples to assure the validity of the run. Quality control samples will be analyzed at specific intervals with each run as specified by the manual of operation for the laboratory performing the analysis. If the quality control materials do not meet the criteria set by the laboratory's manual of operation, the run must be rejected and repeated in total.

E. Longitudinal Control Procedures

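### Whether a thawed lipid sample counts depends on its result, under a 3SD limit that ignores the comparator's variance

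*Protocol*

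**What the plan says.** All references are to the Protocol.

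- **Vials found thawed or leaking at freezer removal (Chapter 8, VII.B).** Here "the sample will be discarded and replaced by another sample that is acceptable". The result plays no part.
- **Samples found thawed on receipt at a laboratory (VII.B).** Those that stayed cold may be assayed for lipids and lipoproteins but not for coagulation factors. For a thawed sample the rule is that it "will not be included in the data analysis if the analytical results are greater than 3SD (biologic plus analytical) from the average". The comparator is the mean of the three remaining draws in the same set.
- **The SDs supplied (VII.B).** The table is headed "Expected biologic plus analytical SD for triplicate analysis" and gives cholesterol 5%, triglyceride 13%, HDL cholesterol 7%, apo A-1 10% and apo B-100 11%. The text does not say whether these describe one result or a mean of three.
- **All other samples (VII.C).** A sample of a set lying more than 3SD "from the average of the others, it will be reanalyzed promptly to confirm the value". No exclusion is stated.
- **Shipping (IV.B and Figure 3).** The four draws of a diet phase go out on the same date, with one bag per participant.

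**The concern.** Two thawed samples with the same handling history are treated differently according to their results: the one that agrees with its neighbours stays and the discordant one goes. Total cholesterol, triglycerides, HDL cholesterol, apo B and apo A-I are primary endpoints under section 1.0.3, so the selection acts directly on endpoint values and makes within-person spread among thawed samples look smaller than it is.

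The rule is also a weak test of damage. A thaw effect that shifts cholesterol by less than the 15% limit can pass unnoticed. Because a participant's four draws travel together, the three comparators may have thawed too. A shift common to all four cancels in the comparison and cannot be detected.

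Finally, the limit compares one value with a mean of three, yet uses the SD as if that mean were known without error. Valid samples are therefore flagged more often than 3SD suggests.

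**Working it through.** **Inputs.** The limit is 3 × the listed SD, applied to one sample against the mean of the other three (VII.B). There are four draws per diet and three diets (Chapter 8, II.A). Fourteen red-capped serum vials are archived per draw (Figure 3). Results are assumed normal and independent within a set. The protocol gives no false-flag rate to reproduce; the two-sided normal tail beyond 3 SD is 0.27%.

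**Limits as written (3 × SD).** Cholesterol 15%, triglyceride 39%, HDL 21%, apo A-1 30%, apo B 33%.

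**Variance of the comparison.** With s the SD of a single sample, SD(x − mean of 3 others) = s × √(1 + 1/3) = 1.155 s.

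**Flag rate for a valid sample, by meaning of the listed SD:**

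| Reading | Effective limit | Flagged |
|---|---|---|
| (a) SD of one sample: 3/1.155 | 2.60 SD | 0.94% |
| (b) Only the assay is triplicated: s² = SD² + (2/3)CV² | 2.56 to 2.24 SD | about 1.0% to 2.5% |
| (c) SD of a mean of three samples: s = √3 × SD, so 3/(√3 × 1.155) = 3/2 | 1.50 SD | 13.4% |

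Reading (b) depends on the assay CV. Cholesterol at 1.1% gives s = √(25 + 0.667 × 1.21) = 5.08 and 1.06%. HDL at an assumed 5% gives s = √(49 + 0.667 × 25) = 8.10 and 2.48%. A simulation of 2,000,000 sets of four agreed for (a) and (c): 0.94% and 13.4%.

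**Relative to 0.27%.** Reading (a) is 0.94/0.27 ≈ 3.5 times and reading (c) is 13.4/0.27 ≈ 49 times.

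**Expected loss of valid results.** This is the flag rate × the number thawed. Per 10 thawed samples: 10 × 0.0094 ≈ 0.1 under (a) and 10 × 0.134 ≈ 1.3 under (c). The number thawed is unknown.

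**Limit that restores 0.27% under (a).** 3 × SD × √(4/3) = 3.46 SD: cholesterol 17.3%, triglyceride 45.0%, HDL 24.2%, apo A-1 34.6%, apo B 38.1%.

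**Spare vials.** Of the 14 red vials, Figure 3 ships at most 6 per draw (phase I: 2 + 2 + 2). Section 3.8.5 takes 2 more for hormone assays in premenopausal women, and Chapter 8, VI.G.3 would take 2 for LDL oxidation if funded. 14 − 6 − 2 − 2 = 4 remain in the worst case.

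**The case against.** The best defence is that exclusion needs two conditions together: a documented handling failure and a discrepant value. Read that way, VII.B salvages compromised samples cautiously. That is right about scope and narrows the point, but inclusion among thawed samples still depends on the endpoint value.

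Several stronger readings are tempting, and the documents do not support them:

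- **Endpoint results in general are dropped for being extreme.** They are not. The exclusion sentence covers thawed samples only, and VII.C sends an intact extreme value for repeat assay.
- **Large numbers of results are lost.** With the example total of 96 in Table 1 there are 96 × 12 = 1,152 draws per analyte, and the flag rates give about 11 under (a) or 154 under (c). These are expected re-assay flags, not discards.
- **The flag rate is 13.4%, with 39% of sets affected.** This needs reading (c), and the source cited for the SDs is not available to confirm it. Nor can one say the rate exceeds what was intended, because no intended rate is stated.
- **Half of the ten primary endpoints lack a limit.** Thawed samples are never assayed for coagulation factors, and LDL is calculated from three listed components. What remains is missing detail: no SD for Lp(a) and, for the VII.C trigger, none for the three coagulation factors.
- **Field staff can delete inconvenient values.** The data system guide (7.6, 2.4 Edits) offers an unresolvable flag "when the value you did collect is suspicious and should not be used in analysis". It is a general status code that leaves a collected value in the database. Hemostasis results arrive in separate files (7.5.2), and principal investigators, coordinators and laboratory technicians are masked (4.4). Bias by this route is not shown.

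**Conclusion.** The point holds for lipid and lipoprotein samples found thawed on receipt. VII.B admits or excludes them by their primary endpoint value, contrary to the value-blind replacement it requires at freezer removal, and against a comparator that may share the same fault.

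The limit is also tighter than its label: 2.60 SD and 0.94% on the reading kindest to the protocol, and more on the other readings tried. The excess over the nominal rate cannot be fixed more closely until the protocol defines its SD. The rates assume normal, independent draws.

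The number of results lost cannot be computed from the documents. It is likely to be small unless thawing is common. The case for change therefore rests on outcome-dependent inclusion, for which the protocol already contains a better rule.

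**What to change.** 1. In VII.B, decide on a thawed sample from the handling record before its result is seen. Replace it with an archived vial from the same draw, as is already required at freezer removal, and delete the 3SD exclusion.
2. In VII.C, set the re-assay trigger at 3 × single-sample SD × √(4/3), and state whether the listed SDs are for one result or a mean of three.

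The cost is revised manual wording, an occasional re-shipment, and one archived vial per replacement. At least 4 of the 14 red vials remain after all listed uses.

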APPENDIX A

INFORMED CONSENT ISSUES

A.1 INFORMED CONSENT ISSUES

A.1 Reasons for Problems in Obtaining Informed Consent

Many trials are unable to achieve their recruitment goals because the investigators fail to obtain informed consent from patients who pass (or would pass) screening examinations. This failure may occur for the following reasons.

1. Culture and tradition of the country, or the investigator's own background, make it emotionally difficult for the investigator to ask patients for their informed consent. The easiest way to resolve this problem is to have someone else ask the patients. This person should be more comfortable with the process and could be another investigator, a nurse, the trial coordinator, or a special resource person (e.g., a translator). For DELTA, it is necessary to limit participants to those who can read and understand English.
2. The investigator who asks for informed consent may be rather stiff or brusque in describing the trial and in asking for the patient's informed consent. In this case, the investigator should spend more time with each patient and not rush the process.

GUIDELINES FOR OBTAINED INFORMED CONSENT

(Taken from Spilker, Bert and Cramer, Joyce A., *Patient Recruitment in Clinical Trials*. New York: Raven Press, 1992.)

A.2 OFFERING PAYMENTS TO RECRUIT VOLUNTEERS OR PATIENTS

A.2.1 Offering Money to Recruit Volunteers

Because volunteers receive no medical benefit from participation in a dietary trial, and are often subjected to severe restrictions in daily living, it is reasonable to pay them for their participation. This is standard practice by many academicians and is accepted as both ethical and appropriate. Money should not be given only to those volunteers who complete an entire trial because this places undue pressure on volunteers to remain in a trial from which they might rather withdraw. Money given to volunteers should be prorated based on the extent of their participation unless there are legal requirements to give all volunteers the entire sum, even for partial participation. The amount of money offered cannot be so excessive that volunteers would feel strong pressure to remain in a clinical trial from which they would rather withdraw.

A.2.2 Basing Payments on Reasons for Leaving a Trial

Subjects may leave a diet study for several reasons. The rigid control of diet over an extended period places severe constraints on daily living. Subjects have given over control of a significant part of their lives to the investigator and study personnel. Inability to comply with these restrictions may make them ineligible to continue with the study. Categories of noncompliance include willful departures from the study diet, severe illness, extended absences for business or personal emergencies. The decision to withdraw a subject involuntarily from the study is made by the Principal Investigator after discussion with the DELTA Steering Committee. Payment to the subject for partial participation is at the discretion of the local field center. If a subject withdraws voluntarily from the study, it is important for the investigator to determine if and to what extent the diet contributed to the dropout. If any link, however remote, is found with the treatment, the situation should be categorized as diet related. Such instances would require full payment to the subject, who provided important data on adverse effects leading to discontinuation of the diet. Not only should the patient or volunteer not feel that he or she disappointed the investigator by stopping the protocol, but each person should be encouraged to report his/her reasons for leaving the study as fully as possible. Subjects who feel vaguely uncomfortable should be encouraged to express this effect rather than deny any problem when asking to withdraw.

Although a subject may not have completed a study for personal reasons, he or she should be given partial payment based on the proportion of the protocol fulfilled. It would be unfair not to provide compensation for activities that might have taken time and effort even if the data cannot be used in study outcome analyses.

A.3 USING COERCIVE TACTICS TO RECRUIT PATIENTS

Any time there is a superior-subservient relationship between two individuals, it is impossible to ensure that coercion was not felt by the person in the subservient position, even if coercion was not overtly used in the recruitment process. Three examples of this relationship in clinical research are (1) an investigator recruiting his or her staff or students, (2) a professor recruiting his or her students, and (3) a pharmaceutical company conducting a clinical trial and recruiting its junior level employees.

Such groups cannot provide a true informed consent if the volunteers believe that refusal to enroll may result in being fired, may affect their career prospects, or influence their course grades.

A.4 ETHICAL GUIDELINES FOR RECRUITMENT OF HEALTHY VOLUNTEERS

1. Use of an informed consent that includes standard elements. The most important element that differs between the vast majority of volunteers and most patients involves the statement that the research is unlikely to be of any direct personal benefit to the volunteer. Similarly, some patients are unlikely to benefit from their participation in a trial.
2. Normal volunteers should not be enrolled in clinical trials where there is perceptible risk. The definition and application of the term risk raises numerous other issues (e.g., how is perceptible risk measured and how much risk is excessive). The balance should be determined by considering the benefits to be gained by society as a whole versus the risks to the individual.
3. Volunteers should not be sought where a dependency relationship exists.
4. Volunteers sought from any organized group should be contacted after officials of that organization have been informed and have fully discussed the issues with those who will conduct the trial.
5. Self-experimentation or experimentation on colleagues or friends of the investigator should be subjected to the same professional and ethical reviews as for other more conventional clinical trials.
6. Issues of liability for injury should be considered and discussed for both negligent causes. It should be determined who is responsible for payment and how payment would be determined. Numerous options and proposals exist in this area (e.g., see Macrae et. al., 1989).

